5 MRI SEQUENCES, CRITERIA FOR EVALUATION, AND DISCIPLINE REVIEWS

5.1 MRI Sequences

For all subject groups images will be acquired on a 3.0 Tesla magnetic field strength scanner.

5.1.1 Brain MRI (Group1):

Subjects should be positioned according to the following protocol. Subjects are allowed to adopt a comfortable position within the head coil before being advanced within the magnet bore. Three slices are acquired in the axial plane by fast spin echo. A coronal slice is prescribed graphically from one of the axial slices showing the falx cerebri. The line cursor is then angled along the midsagittal plane and then rotated 90 degrees. One slice is acquired in this plane. This corrects for right left rotation. A sagittal oblique slice is then prescribed from the coronal oblique. The cursor is angled along the midsagittal plane and one slice is acquired in this plane by spin echo. This corrects for right left cant. From this last image contiguous interleaved slices are prescribed to cover the brain. The

line cursor is angled to pass along the anterior commissure-posterior commissure line (AC-PC line). The localizing scans are saved for reference.

Standard gadolinium contrast MRI will be performed with the following sequences using a SENSE (parallel image) head coil or equivalent. Subjects with renal insufficiency (GFR <50ml/min/1.73m²) or other GBCA contraindication will not undergo an MR with Gadolinium

5.1.1.1 Day 1

Scan type	Scan Time (min)
0. Setup/localizer/B ₀ shimming/B ₁ mapping	2
1. T1-w sagittal FFE (TR300NEX 4) 180mm x 240mm FOV, 192 x 256 matrix, 3 mm contiguous, interleaved	3
2. FLAIR coronal SE/IR (TE109/TR9140/TI2500) 180mm x 240mm FOV, 192 x 256 matrix, 5mm slice thickness, 0.5mm sp	3
3. T1-w axial SE (TE14/TR700 NEX 4) 180mm x 240mm FOV, 192 x 256 matrix, 3 mm contiguous, interleaved	4
4. T2-w axial TSE (TE72/TR9000) 180mm x 240mm FOV, 192 x 256 matrix, 3 mm contiguous, interleaved	2
5. T1-w MPRAGE sagittal 3D TFE (TE3.8/TR8.2/FA8) 230mm x 230mm FOV, 230 x 230 matrix, 1 mm contiguous, interleaved	6
6. Diffusion weighted MRI axial (TE90/TR6000 SE EPI b=0, 500, 1000 s/mm ²) 220mm x 220mm FOV, 128 x 128 matrix, 3 mm contiguous, interleaved	4
7. MRA 3D-TOF (TE3.2/TR18/FA20) 170mm x 200mm x 150 mm FOV 200 x 400 x 140 matrix	5
8. SWI (TE20/TR26/FA15) 198mm x 210mm x 127 mm FOV 248 x 300 x 116 matrix	4
9. PWI T ₂ [*] -w axial; GEPI (TE25/TR1500/FA30) x 100 volumes 220mm x 220mm FOV 128 x 128 matrix, 3 mm contiguous, interleaved Gadoteridol bolus injection 0.1mmol/kg, 3ml/s flow rate.	2
10. T1-w sagittal FFE (TR300NEX 4) 180mm x 240mm FOV, 192 x 256 matrix, 3 mm contiguous, interleaved	3
11. SWI (TE20/TR26/FA15) 198mm x 210mm x 127 mm FOV 248 x 300 x 116 matrix	4
12. T2-w axial TSE (TE72/TR9000) 180mm x 240mm FOV, 192 x 256 matrix, 3 mm contiguous, interleaved	2
13. T1-w axial SE (TE14/TR700 NEX 4) 180mm x 240mm FOV, 192 x 256 matrix, 3 mm contiguous, interleaved	4
14. T1-w MPRAGE sagittal 3D TFE (TE3.8/TR8.2/FA8) 230mm x 230mm FOV, 230 x 230 matrix, 1 mm contiguous, interleaved	6

5.1.1.2 Day 2

Scan type	Scan Time (min)
0. Setup/localizer/B0 shimming/B1 mapping	2
1. T1-w sagittal FFE (TR300NEX 4) 180mm x 240mm FOV, 192 x 256 matrix, 3 mm contiguous, interleaved	3
2. FLAIR coronal SE/IR (TE109/TR9140/TI2500) 180mm x 240mm FOV, 192 x 256 matrix, 5mm slice thickness, 0.5mm sp	3
3. T1-w axial SE (TE14/TR700 NEX 4) 180mm x 240mm FOV, 192 x 256 matrix, 3 mm contiguous, interleaved	4
4. T2-w axial TSE (TE72/TR9000) 180mm x 240mm FOV, 192 x 256 matrix, 3 mm contiguous, interleaved	2
5. T1-w MPRAGE sagittal 3D TFE (TE3.8/TR8.2/FA8) 230mm x 230mm FOV, 230 x 230 matrix, 1 mm contiguous, interleaved	6
6. Diffusion weighted MRI axial (TE90/TR6000 SE EPI b=0, 500, 1000 s/mm ²) 220mm x 220mm FOV, 128 x 128 matrix, 3 mm contiguous, interleaved	4
7. MRA 3D-TOF (TE3.2/TR18/FA20) 170mm x 200mm x 150 mm FOV 200 x 400 x 140 matrix	5
8. SWI (TE20/TR26/FA15) 198mm x 210mm x 127 mm FOV 248 x 300 x 116 matrix	4
9. PWI T2*-w axial; GEPI (TE25/TR1500/FA30) x 100 volumes 220mm x 220mm FOV 128 x 128 matrix, 3 mm contiguous, interleaved ferumoxytol bolus injection 75mg (5ml) 2 fold diluted, up to 3ml/s flow rate. *	2
8. SWI (TE20/TR26/FA15) 198mm x 210mm x 127 mm FOV 248 x 300 x 116 matrix	4
9. PWI T2*-w axial; GEPI (TE25/TR1500/FA30) x 100 volumes 220mm x 220mm FOV 128 x 128 matrix, 3 mm contiguous, interleaved ferumoxytol injection 150mg (10 ml) 2 fold diluted, at 1ml/s flow rate. *	2
8. SWI (TE20/TR26/FA15) 198mm x 210mm x 127 mm FOV 248 x 300 x 116 matrix	4
9. PWI T2*-w axial; GEPI (TE25/TR1500/FA30) x 100 volumes 220mm x 220mm FOV 128 x 128 matrix, 3 mm contiguous, interleaved ferumoxytol injection 285mg (19ml) 2 fold diluted, at 1ml/s flow rate. *	2
10. T1-w sagittal FFE (TR300NEX 4) 180mm x 240mm FOV, 192 x 256 matrix, 3 mm contiguous, interleaved	3
11. SWI (TE20/TR26/FA15) 198mm x 210mm x 127 mm FOV 248 x 300 x 116 matrix	4
12. T2-w axial TSE (TE72/TR9000) 180mm x 240mm FOV, 192 x 256 matrix, 3 mm contiguous, interleaved	2
13. T1-w axial SE (TE14/TR700 NEX 4) 180mm x 240mm FOV, 192 x 256 matrix, 3 mm contiguous, interleaved	4
14. T1-w MPRAGE sagittal 3D TFE (TE3.8/TR8.2/FA8) 230mm x 230mm FOV, 230 x 230 matrix, 1 mm contiguous, interleaved	6

** BP and heart rate check prior to ferumoxytol and after each ferumoxytol injection and 30 minutes after the final ferumoxytol injection*

5.1.1.3 Day 3

Scan type	Scan Time (min)
0. Setup/localizer/B0 shimming/B1 mapping	2
1. T1-w sagittal FFE (TR300NEX 4) 180mm x 240mm FOV, 192 x 256 matrix, 3 mm contiguous, interleaved	3
2. FLAIR coronal SE/IR (TE109/TR9140/TI2500) 180mm x 240mm FOV, 192 x 256 matrix, 5mm slice thickness, 0.5mm sp	3
3. T1-w axial SE (TE14/TR700 NEX 4) 180mm x 240mm FOV, 192 x 256 matrix, 3 mm contiguous, interleaved	4
4. T2-w axial TSE (TE72/TR9000) 180mm x 240mm FOV, 192 x 256 matrix, 3 mm contiguous, interleaved	2
5. T1-w MPRAGE sagittal 3D TFE (TE3.8/TR8.2/FA8) 230mm x 230mm FOV, 230 x 230 matrix, 1 mm contiguous, interleaved	6
6. SWI (TE20/TR26/FA15) 198mm x 210mm x 127 mm FOV 248 x 300 x 116 matrix	4

5.1.2 Spine MRI (Group1)

will be performed on the 3T scanner using SENSE spine coil with the following sequences:

5.1.2.1 Day 1

Scan type	Scan Time (min)
0. Setup/localizer/B0 shimming/B1 mapping	2
1. T1-weighted image Sagittal – Turbo Spin Echo TR=700 msec/TE=10 msec, 3 mm slice thickness, 260mm x 260mm FOV, 320 x 240 matrix	4
2. T1-weighted image Axial – Turbo Spin Echo TR=700 msec/TE=10 msec, 3 mm slice thickness, 180mm x 180mm FOV, 512 x 512 matrix,	4
3. T2-weighted image Sagittal – Turbo Spin Echo TR=4000msec/TE=116 msec, 3 mm slice thickness, 260mm x 260mm FOV, 320 x 240 matrix,	3
4. T2-weighted image Axial – Turbo Spin Echo TR=4000 msec/TE=116 msec, 3 mm slice thickness, 180mm x 180mm FOV, 512 x 512 matrix	3
5. T2*- weighted image Sagittal - Gradient refocused echo (GRE) TR=100 msec/TE=20 msec, 3 mm slice thickness, 260mm x 260mm FOV, 320 x 320 matrix, Flip Angle 10 deg	4
Gadoteridol bolus injection 0.1mmol/kg	1
5. T2*- weighted image Sagittal - Gradient refocused echo (GRE) TR=100 msec/TE=20 msec, 3 mm slice thickness, 260mm x 260mm FOV, 320 x 320 matrix, Flip Angle 10 deg	4
3. T2-weighted image Sagittal – Turbo Spin Echo TR=4000msec/TE=116 msec, 3 mm slice thickness, 260mm x 260mm FOV, 320 x 240 matrix,	4
4. T2-weighted image Axial – Turbo Spin Echo TR=4000 msec/TE=116 msec, 3 mm slice thickness, 180mm x 180mm FOV, 512 x 512 matrix	4
1. T1-weighted image Sagittal – Turbo Spin Echo TR=700 msec/TE=10 msec, 3 mm slice thickness, 260mm x 260mm FOV, 320 x 240 matrix	3

2. T1-weighted image Axial – Turbo Spin Echo TR=700 msec/TE=10 msec, 3 mm slice thickness, 180mm x 180mm FOV, 512 x 512 matrix,	3
5. T2*- weighted image Sagittal - Gradient refocused echo (GRE) TR=100 msec/TE=20 msec, 3 mm slice thickness, 260mm x 260mm FOV, 320 x 320 matrix, Flip Angle 10 deg	4

5.1.2.2

5.1.2.3 Day 2

Scan type	Scan Time (min)
0. Setup/localizer/B0 shimming/B1 mapping	2
1. T1-weighted image Sagittal – Turbo Spin Echo TR=700 msec/TE=10 msec, 3 mm slice thickness, 260mm x 260mm FOV, 320 x 240 matrix	4
2. T1-weighted image Axial – Turbo Spin Echo TR=700 msec/TE=10 msec, 3 mm slice thickness, 180mm x 180mm FOV, 512 x 512 matrix,	4
3. T2-weighted image Sagittal – Turbo Spin Echo TR=4000msec/TE=116 msec, 3 mm slice thickness, 260mm x 260mm FOV, 320 x 240 matrix,	3
4. T2-weighted image Axial – Turbo Spin Echo TR=4000 msec/TE=116 msec, 3 mm slice thickness, 180mm x 180mm FOV, 512 x 512 matrix	3
5. T2*- weighted image Sagittal - Gradient refocused echo (GRE) TR=100 msec/TE=20 msec, 3 mm slice thickness, 260mm x 260mm FOV, 320 x 320 matrix, Flip Angle 10 deg	4
Ferumoxytol : total dose 510mg, diluted 2 fold, given in divided injections: 
 • 5 ml (75mg) at 1ml/sec * • 10 ml (150 mg) at 1ml/sec* • 18 ml (285 mg) at 1 ml/sec* 	1
5. T2*- weighted image Sagittal - Gradient refocused echo (GRE) TR=100 msec/TE=20 msec, 3 mm slice thickness, 260mm x 260mm FOV, 320 x 320 matrix, Flip Angle 10 deg	4
3. T2-weighted image Sagittal – Turbo Spin Echo TR=4000msec/TE=116 msec, 3 mm slice thickness, 260mm x 260mm FOV, 320 x 240 matrix,	4
4. T2-weighted image Axial – Turbo Spin Echo TR=4000 msec/TE=116 msec, 3 mm slice thickness, 180mm x 180mm FOV, 512 x 512 matrix	4
1. T1-weighted image Sagittal – Turbo Spin Echo TR=700 msec/TE=10 msec, 3 mm slice thickness, 260mm x 260mm FOV, 320 x 240 matrix	3
2. T1-weighted image Axial – Turbo Spin Echo TR=700 msec/TE=10 msec, 3 mm slice thickness, 180mm x 180mm FOV, 512 x 512 matrix,	3
5. T2*- weighted image Sagittal - Gradient refocused echo (GRE) TR=100 msec/TE=20 msec, 3 mm slice thickness, 260mm x 260mm FOV, 320 x 320 matrix, Flip Angle 10 deg	4

** BP and heart rate check prior to ferumoxytol and after each ferumoxytol injection and 30 minutes after the final ferumoxytol injection*

5.1.2.4 Day 3

Scan type	Scan Time (min)
0. Setup/localizer/B0 shimming/B1 mapping	2
1. T1-weighted image Sagittal – Turbo Spin Echo TR=700 msec/TE=10 msec, 3 mm slice thickness, 260mm x 260mm FOV, 320 x 240 matrix	4
2. T1-weighted image Axial – Turbo Spin Echo TR=700 msec/TE=10 msec, 3 mm slice thickness, 180mm x 180mm FOV, 512 x 512 matrix,	4
3. T2-weighted image Sagittal – Turbo Spin Echo TR=4000msec/TE=116 msec, 3 mm slice thickness, 260mm x 260mm FOV, 320 x 240 matrix,	3
4. T2-weighted image Axial – Turbo Spin Echo TR=4000 msec/TE=116 msec, 3 mm slice thickness, 180mm x 180mm FOV, 512 x 512 matrix	3
5. T2*- weighted image Sagittal - Gradient refocused echo (GRE) TR=100 msec/TE=20 msec, 3 mm slice thickness, 260mm x 260mm FOV, 320 x 320 matrix, Flip Angle 10 deg	4

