4.5 Ferumoxytol Administration: Route and Dosing

Ferumoxytol will be injected intravenously in divided doses followed by a saline flush. The maximum total dose during the day 2 MRI will be 510mg Fe. Ferumoxytol will be diluted in normal saline (1:1 or 15mg/ml) to reduce T2* effects in the MR angiography. [126] The drug will be stored at room temperature (68-77° F) away from direct sunlight. The solution will be prepared and dispensed by the investigational drug pharmacist. It will be administered in an OHSU MR suite.

For acquisition of DSC-MRI data, ferumoxytol (5 ml=75 mg) will be injected at up to 3 ml/sec followed by a saline flush. This rate is required for adequate signal change during the dynamic imaging. When no DSC-MRI data is obtained (spine and Group 3, the rate of the first dose (5 ml=75mg) will be 1 ml/sec. The remainder of the dose will be given in a second (10 ml=150 mg) and third (19 ml=285 mg) injection at a lower flow rate, not faster than 1 ml/s. There will be a short break in time between the three injections to allow for assessment per sections 4.7.5 and 5.1. *The dilution and injection parameters of the ferumoxytol may be adjusted to obtain optimal signal changes on MRI/MRA and to decrease the possibility of an allergic reaction. Injection rate can be varied based on the participant's IV site, but the total dose will never exceed 510mg.*

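### The 1-minute spine Day 2 injection row is inconsistent with the assessment breaks in 4.5 and with the 5-minute row for the same regimen in Group 3; the break has no minimum length or explicit hold, and 18 ml should read 19 ml.

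*Combined protocol and SAP*

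**What the plan says.** Section 4.5 sets the regimen: 75, 150 and 285 mg in 5, 10 and 19 ml at 15 mg/ml, not above 510 mg in total. For spine and lymph-node imaging the first dose is slowed too: "When no DSC-MRI data is obtained (spine and Group 3, the rate of the first dose (5 ml=75mg) will be 1 ml/sec". The last is the "third (19 ml=285 mg) injection at a lower flow rate, not faster than 1 ml/s". On spacing, 4.5 says: "There will be a short break in time between the three injections to allow for assessment per sections 4.7.5 and 5.1". It also mentions a flush ("Ferumoxytol will be injected intravenously in divided doses followed by a saline flush") without a volume, and without saying whether one follows each injection.

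Section 4.7.5 asks for blood pressure and heart rate no later than 10 minutes after each injection. It adds that data points are flexible because safety in the magnet comes first.

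The spine Day 2 table (5.1.2.3) lists the dose in one row ("Ferumoxytol : total dose 510mg, diluted 2 fold, given in divided injections") with 1 in the scan-time column. The third injection is printed as "18 ml (285 mg) at 1 ml/sec". The footnote requires a "BP and heart rate check prior to ferumoxytol and after each ferumoxytol injection and 30 minutes after the final ferumoxytol injection". The Group 3 Day 2 table (5.1.6.2) prints the same three volumes and rates, including 18 ml, but allots 5 minutes.

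**The concern.** Two tables give the same three injections at the same rate 1 minute and 5 minutes. The shorter entry leaves little room for the assessment that 4.5 places between injections.

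Spacing matters because of the role that fractionation has in this plan. Section 2.6.2.2 reports that the boxed warning removed the fast undiluted injection over about 1 minute and recommended at least 15 minutes. The plan's answer is three separate doses, with the argument that several injections may be safer than a continuous one. That argument is stronger if each gap is long enough to notice a reaction. It is weaker if a schedule can be read as putting all three doses into about a minute, in a session with no dynamic acquisition that needs speed.

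The 18 ml entry is a separate slip. It matters because it is a volume that staff would draw up.

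**Working it through.** **Inputs.** Spine row: 1 min, and 5, 10 and 18 ml at 1 ml/s (5.1.2.3). Third volume of 19 ml and concentration of 15 mg/ml (4.5). Group 3 row: 5 min (5.1.6.2). Check window: 10 min (4.7.5).

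**1. The plan's figure.** Flow time = volume / rate.
- As printed: (5 + 10 + 18) / 1 = 33 s.
- With 19 ml: (5 + 10 + 19) / 1 = 34 s.

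The 1 minute is consistent with bare flow time rounded up. A figure that includes breaks, checks and flush cannot be reproduced, because their durations are not given.

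**2. Time left per gap.** There are two gaps between three injections.
- Spine: (60 − 34) / 2 = 13 s, or (60 − 33) / 2 = 13.5 s.
- Group 3: (300 − 34) / 2 = 133 s, about 2.2 min.

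The spine row therefore holds a check in each gap only if flush, reading and assessment together take about 13 s.

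**3. Sensitivity to what is not stated.** Assumptions: one reading takes 15 to 60 s, and each injection is followed by 0 to 20 ml of flush at 1 ml/s. The upper volume is the one described for earlier local sessions in 2.6.2.2, which ran at 3 ml/s. Total = flow + 3 × flush + 2 × reading.
- Low end: 33 + 0 + 30 = 63 s.
- High end: 34 + 60 + 120 = 214 s.

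Over this range the total exceeds 60 s, narrowly at the low end, and fits 300 s with at least 300 − 214 = 86 s to spare.

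**4. The 10-minute window against the scheduled spacing on Day 2.**

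| Table | Spacing |
|---|---|
| Brain (perfusion 2 + SWI 4) | about 6 min |
| Carotid, aortic (one MRA row) | 3 min |
| Group 3 | about 2.2 min |
| Spine | about 13 s |

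Each is shorter than 10 minutes. The lower-extremity table (5.1.5.3) has no injection row, so no spacing can be derived. A reading could thus meet 4.7.5 and still be taken after the next injection. Section 4.5 points the other way, because it places the assessment in the break, but it refers to 4.7.5 for the content of that assessment.

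**5. Volume.** The first two doses confirm the concentration: 75/5 = 15 and 150/10 = 15 mg/ml. At 15 mg/ml, 18 ml is 270 mg, and 285 mg needs 285/15 = 19 ml. The printed total is 33 × 15 = 495 mg, short by 15 mg, and 15/510 = 2.9%. The brain, carotid and aortic tables use 19 ml.

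**6. Session length.** The spine Day 2 rows sum to 2+4+4+3+3+4+1+4+4+4+3+3+4 = 43 min. With a 5-minute row: 43 − 1 + 5 = 47 min. The brain Day 2 rows sum to 66 min.

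**The case against.** The strongest reply is that the column records scan time, not elapsed time. No Day 2 table gives a row to any vital-sign check, including the baseline check and the one 30 minutes after the last injection that the same footnote requires. Read as a full time budget, every Day 2 table would fail. The single gadolinium injection in the spine Day 1 table ("Gadoteridol bolus injection 0.1mmol/kg") is also timed at 1 minute, which suggests a nominal entry. Section 4.7.5 allows flexible timing, and the end of 5.1 says that sequences may change.

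Much of this stands. A reader might infer that the slot cannot hold the checks. The documents do not support that, because reading time and flush volume are not stated and the cell may be nominal. A reader might also infer that nothing puts the check before the next injection. That is wrong too, because 4.5 places an assessment between the injections, and the outer limit in 4.7.5 does not cancel it.

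The inconsistency remains. If the cell is nominal, the same regimen should not read 1 minute in one table and 5 in another. Flexibility permits a longer gap but does not require one, and it equally permits a later check.

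**Conclusion.** The point holds as an inconsistency with two small gaps. The spine row leaves about 13 s per gap before any flush, against about 133 s for the same regimen in Group 3. Section 4.5 requires the break but gives no minimum length and no condition that stops the next injection. The 18 ml entry is a plain error in two tables.

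The 13 s figure uses only printed volumes, rates and the 1-minute entry. The statement that a check would overrun rests on the assumed 15 to 60 s per reading.

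A reader might go further and infer that spine subjects will receive 510 mg in a minute, or face a marked excess risk. The first follows only if the table cell overrides 4.5. The second is not shown: 2.6.2.2 reports no grade 4 or 5 toxicity attributed to ferumoxytol in 671 local infusions at a faster flow rate, although it does not state the time between boluses. Nor is the volume slip a safety excess, since it lowers the dose by 2.9%.

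The changes are still worth making. They concern what staff draw up and when they inject, and they support the fractionation on which the plan's response to the boxed warning relies.

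**What to change.** 1. In 5.1.2.3, set the injection row to 5 minutes, as in 5.1.6.2.
2. Add one sentence to 4.5 and 4.7.5: no further injection starts until blood pressure, heart rate and symptoms after the previous injection are recorded and acceptable. Keep 10 minutes as an outer limit. The rule would apply to all groups, including the lower-extremity table, which lists no injection times.
3. Change 18 ml to 19 ml in 5.1.2.3 and 5.1.6.2.

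**Cost.** About 4 minutes per spine Day 2 session (43 to 47 scheduled minutes), one sentence in two places, and one digit in each of two tables. The readings are already required. The added time is well short of the 15-minute scanner stop that 2.6.2.2 considers disadvantageous. Sequences, endpoints and the intended 510 mg dose do not change.

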5.1.3 Carotid MRA and plaque imaging (Group2)

Carotid imaging will be performed using a SENSE spine coil with activation of the cervical segments or a surface coil to take advantage of maximal signal received in the proximity of the carotids. To reduce pulsation artifacts, imaging of carotid plaques will be acquired using a cardiac gating technique. Since there have been no established imaging sequences for ferumoxytol for this indication, the sequences will be tested by repeating various imaging sequences by altering imaging parameters and acquiring images multiple times. MR sequences are subject to change.

5.1.3.1 Day1

Scan type	Scan Time (min)
0. Setup/localizer/B0 shimming/B1 mapping	2
1. Axial T1-weighted (T1w) gradient-recalled-echo (GRE)	4
2. Axial and/or oblique sagittal T2*-weighted gradient-echo (GRE) Frequency-selective prepulse for fat suppression	4
3. Axial proton-density-weighted (PDw) fast spin-echo (PDw FSE) Frequency-selective prepulse for fat suppression	3
4. Cervical MRA: 3D T1 Fast Field Echo, 25° Flip Angle, TR=5.5 msec/TE=1.3 msec 1-1.5 mm slice thickness in the coronal plane Gadoteridol bolus injection 0.1 mmol/kg 3ml/s flow rate	3
5. Axial T1-weighted (T1w) gradient-recalled-echo (GRE)	4
6. Axial and/or oblique sagittal T2*-weighted gradient-echo (GRE) Frequency-selective prepulse for fat suppression	4
7. Axial proton-density-weighted (PDw) fast spin-echo (PDw FSE) Frequency-selective prepulse for fat suppression	3

5.1.3.2 Day 2

Scan type	Scan Time (min)
0. Setup/localizer/B0 shimming/B1 mapping	2
1. Axial T1-weighted (T1w) gradient-recalled-echo (GRE)	4
2. Axial and/or oblique sagittal T2*-weighted gradient-echo (GRE) Frequency-selective prepulse for fat suppression	4
3. Axial proton-density-weighted (PDw) fast spin-echo (PDw FSE) Frequency-selective prepulse for fat suppression	3
4. Cervical MRA: 3D T1 Fast Field Echo, 25° Flip Angle, TR=5.5 msec/TE=1.3 msec 1-1.5 mm slice thickness in the coronal plane Ferumoxytol injection 75mg (5ml) up to 3ml/s flow rate	3
5. Cervical MRA: 3D T1 Fast Field Echo, 25° Flip Angle, TR=5.5 msec/TE=1.3 msec 1-1.5 mm slice thickness in the coronal plane Ferumoxytol injection 150mg (10ml) at 1ml/s flow rate	3
6. Cervical MRA: 3D T1 Fast Field Echo, 25° Flip Angle, TR=5.5 msec/TE=1.3 msec 1-1.5 mm slice thickness in the coronal plane Ferumoxytol injection 285mg (19 ml) at 1ml/s flow rate	3
7. Axial T1-weighted (T1w) gradient-recalled-echo (GRE)	4
8. Axial and/or oblique sagittal T2*-weighted gradient-echo (GRE) Frequency-selective prepulse for fat suppression	4
9. Axial proton-density-weighted (PDw) fast spin-echo (PDw FSE) Frequency-selective prepulse for fat suppression	3

** BP and heart rate check prior to ferumoxytol and after each ferumoxytol injection and 30 minutes after the final ferumoxytol injection*

5.1.3.3 Day 3 (48h post ferumoxytol)

Scan type	Scan Time (min)
0. Setup/localizer/B0 shimming/B1 mapping	2
1. Axial T1-weighted (T1w) gradient-recalled-echo (GRE)	4
2. Axial and/or oblique sagittal T2*-weighted gradient-echo (GRE) Frequency-selective prepulse for fat suppression	4
3. Axial proton-density-weighted (PDw) fast spin-echo (PDw FSE) Frequency-selective prepulse for fat suppression	3

5.1.3.4 Day 4 (1week post ferumoxytol) (at physician's discretion)

Scan type	Scan Time (min)
0. Setup/localizer/B0 shimming/B1 mapping	2
1. Axial T1-weighted (T1w) gradient-recalled-echo (GRE)	4
2. Axial and/or oblique sagittal T2*-weighted gradient-echo (GRE) Frequency-selective prepulse for fat suppression	4
3. Axial proton-density-weighted (PDw) fast spin-echo (PDw FSE) Frequency-selective prepulse for fat suppression	3

5.1.4 Aortic MRA and wall imaging

Aortic imaging will be performed using a cardiac surface coil (receiver) and a body coil (transmission). To reduce pulsation artifacts, imaging will be acquired using a cardiac gating technique. Since there have been no established imaging sequences for ferumoxytol for this indication, the sequences will be tested by repeating various imaging sequences by altering imaging parameters and acquiring images multiple times. MR sequences are subject to change.

